Title: Comparison of a Novel Head-Mounted Perimeter versus the Humphrey Field Analyzer

Principal Investigator: [name]

NCT #: NCT05674890

Date: July 10, 2024

VR Headset vs HVF

PI: [name] IRB ID #: 202206347

Project Details

I. Project Introduction

I.1 Project to be reviewed by:

IRB-01

I.2 Project Title:

Comparison of a Novel Head-Mounted Perimeter versus the Humphrey Field Analyzer

I.3 Short Title (optional):

VR Headset vs HVF

- 1.4 Provide a short summary of the purpose and procedures of the study proposed in this IRB application.
 - DO NOT include information on studies not proposed in this application.
 - Use LAY terminology only. This must be easily understandable by IRB community members and nonscientists.
 - DO NOT cut and paste technical abstracts from funding applications that may not be understood by a general audience.

The purpose of this prospective study is to compare the novel Smart System VR Headset (M&S Technologies, Niles, IL) to the current accepted gold standard Standard Automated Perimeter, the Humphrey Field Analyzer (Carl Zeiss Meditec Inc., Dublin, CA). Use of the Humphrey Field Analyzer is the standard of care and would be completed regardless of study participation if clinically indicated.

The proposed study will be conducted at the University of Iowa Hospitals and Clinics. We estimate 50 subjects will be recruited to participate in the study. Data collected will not include patient identifiers.

Research involves retrospective collection of data, documents, and records, as well as prospective collection of visual field testing performance. The source of data will be retrospective review of computerized or written medical record and testing conducted in clinic beginning upon IRB approval. Patients with suspected, mild, moderate, or severe glaucoma will be included. Clinical data including age, gender, ethnicity, visual acuity, intraocular pressure, severity of disease, Humphry Visual Field performance, Pico VR Visual Field performance, and satisfaction survey will be recorded.

Subjects will undergo regular clinical examination, including measurement of visual acuity, intraocular pressure, slit lamp examination by their physician, and visual field testing as indicated. When it comes time to perform visual field testing, subjects will be randomized to complete either the Pico VR Headset visual field test first followed by the Humphrey Field Analyzer visual field test, or vice versa. Visual field tests will be separated by a rest period of one hour to minimize testing fatigue.

The Smart System VR Headset is fit to subjects' head using an adjustable head strap. Once the headset it fit to the subject, a research assistant will send a test to the headset from a bluetooth-connected electronic device using M&S Technologies' secured application platform. Subjects will follow prompts from the Smart System VR Headset to complete their visual field test, responding using a handheld "trigger" device. Testing is expected to take approximately 5-10 minutes, depending on the subjects' severity of visual field loss. Following visual field testing using both the Smart System VR Headset and Humphrey Field Analyzer, subjects will complete a 13-question satisfaction survey. The total expected time commitment of this study is an additional 1.5-2 hours to the subjects' regular clinical appointment.

M&S Technologies is the developer of the Smart System VR Headset visual field test. [name], [name], and [name] have no financial or intellectual relationship with M&S Technologies, aside from the current study and an additional study under IRB review investigating the EyeSimplify visual field test.

As the developers of the Smart System VR Headset visual field test, M&S Technologies maintains a secure, encrypted, HIPAA-compliant database of Smart System VR Headset users. This database includes patient profiles containing unique subject IDs (de-identified), birth year, and visual field testing results. Outside of this testing information, M&S Technologies does not have access to any additional patient information.

1.5 Specify your research question(s), study aims or hypotheses (do not indicate "see protocol")

Aim 1: Compare the performance of the Smart System VR Headset to the Humphrey Visual Field Analyzer

Aim 2: Determine the subjective perception of ease of use of the Smart System VR Headset

Primary Hypothesis: The Smart System VR Headset (M&S Technologies, Niles, IL) will perform as well as or better than the Humphrey Visual Field Analyzer (Carl Zeiss Meditec Inc., Dublin, CA) in identifying glaucomatous visual field changes.

I.6 Background and significance and/or Preliminary studies related to this project. (do not indicate "see protocol")

Glaucoma is the leading cause of irreversible blindness worldwide (1-2). Standard Automated Perimetry with the Humphrey Visual Field Analyzer (HFA; Carl Zeiss Meditec Inc., Dublin, CA) is the current accepted clinical standard for diagnosis and monitoring of glaucomatous visual field loss (3). Despite ubiquitous use, the HFA has several disadvantages that limit its utility. The HFA is a large, expensive device that requires dedicated clinic space. It is immobile, so bedside examination and home monitoring are not possible. Additionally, it is difficult for patients with limited mobility or large body habitus to comfortably position themselves for the duration of the exam. Recently, there has been interest in development of a head-mounted virtual reality perimeter to address these limitations (4-6).

I.7 Literature cited / references (if attaching a grant or protocol enter N/A).

- 1. Quigley HA. Number of people with glaucoma worldwide. Br J Ophthalmol. May 1996;80(5):389-93. doi:10.1136/bjo.80.5.389

II. Research Team

II.1 Principal Investigator

Name E-mail College
[name] Carver College of Medicine

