The Principal Investigator will identify subjects that meet inclusion criteria based on chart review prior to potential subjects' upcoming glaucoma clinic appointments. Potential subjects will be approached at the time of their scheduled appointment to participate in the study. The Principal Investigator and/or research assistant will describe the purpose of the study, study procedure, and risks/benefits of participation prior to obtaining informed consent from the subject. Additionally, the Principal Investigator and/or research assistant will reassure potential subjects that their participation in the study is completely voluntary, they are free to withdraw from the study at any point without consequences, and their decision to participate/not participate will not affect their regular care.

VII.D.37 Does the study include any form of deception (e.g., providing participants with false information, misleading information, or withholding information about certain study procedures)?

Examples:

- Procedure includes a cover story that provides a plausible but inaccurate account of the purposes of the research.
- Participants will be provided with false information regarding the particular behaviors of interest in the research.
- Procedures include a confederate pretending to be another participant in the study.
- Participants will be told that the research includes completion of a particular task, when in fact, that task will not be administered.
- Study is designed to introduce a new procedure (or task) that participants are not initially told about.
- If yes, a waiver of informed consent must be requested under question IV.3.

No

VII.E. Project Description (E)

- VII.E.1 Will subjects be randomized?
 - VII.E.1.a Will any subjects be blinded to which study arm they have been assigned?
 No
 - VII.E.2 Describe randomization scheme/assignment including ratio such as 1:1, 2:1 etc.
 Patients will be randomized in a 1:1 ratio to either perform Humphrey Visual Field testing followed by Smart System VR Headset testing or vice versa.
- VII.E.3 Will any questionnaires, surveys, or written assessments be used to obtain data directly from subjects in this study?
 Yes

- VII.E.4 List all questionnaires, surveys, written assessments and ATTACH each one to the application. (NOTE: You are NOT prohibited from attaching copyrighted materials to this application)
 Smart System VR Headset satisfaction survey

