- VII.E.5 Does this project involve creating any audiotapes, videotapes, or photographs?
- VII.E.6 Provide a detailed description in sequential order of the study procedures following the consent process DO NOT cut and paste from the Consent Document.

Describe study populations separately if they will be participating in different procedures - include CONTROL population if applicable.

DESCRIBE:

- What subjects will be asked to do/what happens in the study (in sequential order)
- The time period over which procedures will occur
- The time commitment for the subject for individual visits/procedures
- Long-term followup and how it occurs

Potential subjects will be approached at the time of their regularly scheduled appointment to participate in this research study. The research assistant will answer any questions potential subjects may have regarding the purpose, procedure, and risks of the study. If they agree to participate, subjects will sign an informed consent.

In addition to routine clinical examination including measurement of visual acuity, tonometry, and slit lamp examination, subjects will undergo perimetry with both the Smart System VR Headset (SSVR) and the Humphrey Field Analyzer (HFA). If the subject requires pupillary dilation during their appointment, visual field testing (VF) will be conducted prior to dilation. Subjects will be randomized to perform either the SSVR VF followed by the HFA VF or vice versa. Both VF will occur on the same day with a 15-20 minute break between tests at the University of Iowa Hospitals and Clinics' Glaucoma clinic. The total additional time commitment of study participation is expected to be 1-2 hours.

The SSVR Headset uses a 24-2 examination protocol with a Neighborhood-Zippy Estimation by Sequential Testing (ZEST) testing algorithm. Background brightness will be set to 15.8 ASB. The test will use Goldmann size III stimulus. The research assistant will administer the SSVR VF. The SSVR VF will be deemed unreliable if FP >25%. The HFA uses a 24-2 examination protocol with a SITA standard testing algorithm. A clinical technician will administer the HFA VF. The HFA VF will be deemed unreliable if FP >15%. After completing both VF tests, subjects will complete a satisfaction survey regarding the SSVR.

VII.E.7 Will you attempt to recontact subjects who are lost to follow-up?

No - those lost to followup will not be recontacted

VII.E.9 Will subjects be provided any compensation for participating in this study?

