 investigator's office by a research team member where they will be stored in a locked file cabinet until the conclusion
 of the study.
 - Electronic records (computer files, electronic databases, etc.) All electronic files will be kept as files on an encrypted, password-protected UIHC Department of Ophthalmology network server. There will be no identifiers or link available on any transferred data; therefore, there will be no way to compromise patients' privacy or confidentiality. M&S Technologies receives subject demographic and testing data upon completion of testing using the Smart System VR Headset. This data is stored in a secure, encrypted, HIPAA-compliant database. Subject names are not stored. Instead, Subjects receive encrypted ID codes.
 - Name -
 - Title Senior IT Support Consultant
 - University Job Classification Faculty/Staff
- X.5 Do the confidentiality protections indicated above allow only members of the research team to access the data/specimens?

X.6 Describe

M&S Technologies, the developers of the Smart System VR Headset visual field test, maintain a secure, encrypted, HIPAA-compliant database of patient testing information. This database includes study ID (de-identified), birth year, and experimental visual field testing data. M&S Technologies does not have access to any additional patient information.

X.7 Does your study meet the NIH criteria for a Certificate of Confidentiality or will you be applying for Certificate of Confidentiality?

No

XI. Data Analysis

XI.1 Describe the analysis methods you will use, including, if applicable, the variables you will analyze Variables: Clinical data including age, gender, ethnicity, visual acuity, intraocular pressure, Humphry Visual Field performance, Smart System VR Visual Field performance, and satisfaction survey will be collected and analyzed.

Data analysis: Humphrey Visual Field and Smart System VR Visual Field performance will be analyzed using pointwise comparisons grouped according to the Garway-Heath structure-function map.

XI.2 Provide the rationale or power analysis to support the number of subjects proposed to complete this study. Power analysis calculation summary:

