Sample sizes of 80 on device one (Smart System VR Headset) and 80 on device two (Humphrey Field Analyzer), which were obtained by sampling 40 clusters for device one and 40 clusters for device two with an average of 2 subjects per cluster, achieve 87% power to detect a difference between the device means of at least 0. The standard deviation of subjects is 0.25. The intracluster correlation coefficient is 0.500. A test based on a mixed-model analysis is anticipated at a significance level of 0.050. Here we view cluster one as testing using device one before device two and cluster two as testing on device two before device one.

A full version of the power analysis calculation has been attached as an additional document to the IRB - there was some difficulty with formatting when transferring this calculation from our statistician's text document to the IRB form.

XII. Future Research

- XII.1 Do you wish to keep any information about subjects involved with this research project so that members of the current research team may contact them in the future for your own research projects?

 No
- XII.2 Do you wish to keep any information about subjects involved with this research project so that other researchers may contact them for future research?

 No
 - XII.4 Does this project involve storing any data, tissues or specimens for future research? Yes—contribution for future use is mandatory for participation in the study

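### The primary hypothesis claims the headset does at least as well as HFA, but the only test described looks for a difference in means, and the public text gives no rule for concluding success

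*Combined protocol and SAP*

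**What the plan says.** - **Hypothesis (I.5).** The headset "will perform as well as or better than the Humphrey Visual Field Analyzer" in identifying glaucomatous visual field changes. Aim 1 in the same section is only to compare the two devices.
- **Analysis (XI.1).** Field results from the two devices "will be analyzed using pointwise comparisons grouped according to the Garway-Heath structure-function map". No test, estimate, interval or decision rule is attached to this.
- **Power (XI.2).** The stated sample sizes "achieve 87% power to detect a difference between the device means". They come from "40 clusters for device one and 40 clusters for device two with an average of 2 subjects per cluster", with SD 0.25 and intracluster correlation 0.500. The section continues: "A test based on a mixed-model analysis is anticipated at a significance level of 0.050". It then describes the clusters by test order.
- **Attachment (XI.2).** "A full version of the power analysis calculation has been attached as an additional document to the IRB", because of formatting trouble in the transfer.
- **Design (VII.E.2, VII.E.6).** Patients are randomized 1:1 to "Humphrey Visual Field testing followed by Smart System VR Headset testing or vice versa", so each patient is tested on both devices.
- **Reference (I.4).** HFA is described as the accepted gold standard. No other reference for glaucomatous change is named in the analysis.
- **Other documents (VII.B.11).** There is no separate written protocol, so this form is the plan.

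**The concern.** The hypothesis needs evidence that the headset is not meaningfully worse than HFA. A test of no difference supplies evidence of the opposite kind: rejection shows that the devices differ, and non-rejection shows only that the data did not separate them. A small or noisy study would therefore tend to support the hypothesis by default, and a precise one could seem to refute it through a trivial difference.

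The outcome does not match either. The hypothesis concerns identifying field changes, while the powered quantity is a mean with no stated unit. No normal/abnormal classification is defined.

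Section IX.2 gives validation of a head-mounted perimeter as the benefit to society, and VII.B.32 says that this headset has no prior studies. The plan does not say which result would count as validation, and a margin chosen after seeing the data would carry little weight.

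**Working it through.** **Inputs from XI.2:** SD 0.25, ICC 0.5, 40 clusters of 2 per device (80 tests per device), alpha 0.050, power 87%. Two-sided testing is assumed because sidedness is not stated. The detectable difference is not legible in the text, so it is back-solved below.

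**1. The plan's own figure.** The design effect is 1 + (2 − 1) × 0.5 = 1.5, so the effective sample per device is 80 / 1.5 = 53.3. SE = 0.25 × √(2 / 53.3) = 0.0484. The difference giving 87% power is (1.960 + 1.126) × 0.0484 = 0.149. As a check, a difference of 0.15 gives Φ(0.15 / 0.0484 − 1.960) = 87.3%. So 87% is consistent with a two-sided test for a *difference* of about 0.15, treating the devices as independent samples. The 0.15 is inferred.

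**2. Reading non-significance as doing as well.** For a true deficit d, the chance of a non-significant result is Φ(1.960 − d/SE) − Φ(−1.960 − d/SE).

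The paired columns are a sensitivity range resting on assumptions: clusters are 40 patients with two eyes each, and the between-device correlation (same eye / opposite eye) is 0.5/0.25 or 0.7/0.4. With those, SE² = 2 × 0.25² × (1.5 − r_same − r_opposite) / (2 × 40), giving SE 0.0342 and 0.0250.

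| True deficit | Unpaired, SE 0.0484 | Paired 0.5/0.25, SE 0.0342 | Paired 0.7/0.4, SE 0.0250 |
|---|---|---|---|
| 0.05 | 82% | 69% | 48% |
| 0.10 | 46% | 17% | 2% |
| 0.15 | 13% | 0.8% | under 0.1% |

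The chance of passing a given deficit depends on the SE, and so on sample size and correlation. It is not controlled at any chosen level.

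**3. What a proper rule would give.** Under an equivalence rule (95% CI wholly within ±M) and a true difference of 0, power is 2Φ(M/SE − 1.960) − 1. The margins are illustrations only.

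| M | Unpaired | Paired 0.5/0.25 | Paired 0.7/0.4 |
|---|---|---|---|
| 0.10 | 8% | 66% | 96% |
| 0.15 | 2 × 0.8725 − 1 = 75% | 98% | over 99% |

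If the aim is estimation, the 95% CI half-width is 1.96 × SE: 0.095 unpaired, 0.067 or 0.049 paired.

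**The case against.** **The attachment may hold what is missing.** It could define the outcome, the detectable difference or even a margin. This stands as a limit: the finding concerns the public text, and the attachment should be read first. But the XI.2 summary of that calculation describes a difference test, and a detectable difference is not a declared margin.

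**The illustration depends on assumptions.** The deficits and correlations have no source in the plan, and at the difference the plan was apparently sized for (about 0.15) the test misses only 13%, or under 1% if paired. This also stands. The figures show the mechanism, not the trial's actual error rate. Two eyes per patient is likewise an assumption: XI.2 describes clusters by test order, and no section says both eyes are analysed.

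**Little is at stake clinically.** VIII.2 says that no treatment is directed by the study, and Aim 1 is only to compare. That argues for allowing a softer hypothesis, not for leaving the present one with a test that cannot support it.

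**Stronger readings that the documents do not support.**
- A reader might infer that the sample is too small. That cannot be judged without a margin and a between-device correlation; step 3 spans 8% to over 99%.
- A reader might take the printed detectable difference of zero as an error in the plan. XI.2 itself reports formatting trouble, so no weight is put on it.
- A reader might conclude that a one-sided non-inferiority test, with higher values counted as better, is the natural cure. If the outcome is threshold sensitivity, a headset that reads systematically too high would pass that rule while missing defects, which is contrary to a hypothesis about identifying change.

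**Conclusion.** The concern holds and should be fixed before analysis. As described in the public text, the difference test cannot support the primary hypothesis, whatever its result. This is a mismatch between claim and analysis, not merely missing detail. A margin, an agreement criterion and a success rule are all absent from XI.1 and XI.2. The claim of better identification also has no stated basis, because HFA is the only reference named.

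On size: under the plan's unpaired layout, true deficits of 0.05, 0.10 and 0.15 would go undetected 82%, 46% and 13% of the time. Pairing lowers these by an amount that depends on a correlation the plan does not state. The logical point needs none of these numbers; it rests only on the wording of I.5, XI.1 and XI.2, subject to what the attachment contains.

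**What to change.** 1. **Check the attached power calculation** for an outcome, unit, detectable difference and any margin, and bring these into the plan.
2. **XI.1.** Name one primary outcome. Base the primary conclusion on the within-patient headset-minus-HFA difference with its 95% CI, from a model that respects the pairing, and the clustering of eyes within patient if both eyes are used. Conclude that the headset does as well only if the whole CI lies within a two-sided equivalence margin, fixed and justified in the outcome's units before analysis. Keep the Garway-Heath sectors as supporting results. Do not use a one-sided higher-is-better rule on sensitivity.
3. **If the claim about identifying change stays,** define a normal/abnormal classification and report positive and negative agreement with HFA, with patient-clustered CIs. Drop the claim of doing better.
4. **Alternatively,** reword I.5 as estimation of agreement between the devices, which needs no margin.
5. **XI.2.** Restate power (or CI width, for estimation) for the chosen rule and the paired design, with the assumed between-device correlation.

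**Cost:** rewording of I.5, XI.1 and XI.2, an outcome definition, and either agreement on a margin in advance or a softer claim. The stated 87% may change in either direction. No new measurements are needed, since every patient already takes both tests.

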VI.6	How ma 0	ny minor subjects do you expect to consent or enroll for this project?
VI.13	Describe	EACH of your subject populations
		clude description of any control group(s) ecify the Inclusion/Exclusion criteria for EACH group
	Inclusion	criteria: Patients older than 18 years of age with suspected, mild, moderate, or severe glaucoma
	corrected	n criteria: Non-english speakers, patients with systemic or ocular disease affecting central vision (including best visual acuity less than 20/80), neurocognitive or psychiatric patients that are unable to perform testing, sm >+2.00/-2.00 diopters
VI.14		un estimate of the total number of subjects that would be eligible for inclusion in each of your study populations your control population if applicable)
VI.15		how you will have access to each of your study populations in sufficient number to meet your recruitment
		at the University of Iowa Hospitals and Clinics' Glaucoma clinic will be approached at the time of their scheduled aents to participate in this research study.
VI.16	Do you p No	elan to recruit/enroll non-English speaking people?
VI.18	Do you p	propose to enroll any of the following in this study as subjects?
	• Inc	uployee of the PI or employee of a research team member dividual supervised by PI or supervised by member of research team dividual subordinate to the PI or subordinate to any member of the research team udent or trainee under the direction of the PI or under the direction of a member of the research team
	No	
VI.20	Will subj No	ects provide any information about their relatives?
VI.23	Will any No	one (other than the subject) provide you with information about the subject (e.g. proxy interviews)?
VI.26	Is this pr No	oject about pregnant women?
VI.27	Will this No	project involve fetuses?
VI.28		s project involve adult subjects who may be incompetent or have limited decision-making capacity on initial int into the study?
VI.32	Does this No	s project involve subjects whose capacity to consent may change over the course of the study?

VII.A. Project Description (A)

No

VI.37

VII.A.1 Where will project procedures take place (check all that apply)?

Does this project involve prisoners as subjects?

• UIHC - Glaucoma clinic

VII.A.2 Is this project also being conducted by other researchers at their own sites (e.g. a multi-site collaborative project)?

No

VII.B. Project Description (B)

VII.B.

VII.B.1.

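### The primary hypothesis allows a claim that the headset detects glaucomatous change better than the Humphrey, but with the Humphrey as sole reference and a difference-in-means test, neither *better* nor *as well as* can be shown

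*Combined protocol and SAP*

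**What the plan says.** - **Hypothesis (I.5).** The headset "will perform as well as or better than the Humphrey Visual Field Analyzer" "in identifying glaucomatous visual field changes". Aim 1 in the same section is neutral: it only compares the performance of the two devices.
- **Reference.** The summary (I.4) describes the Humphrey as "the current accepted gold standard Standard Automated Perimeter". The background (I.6) says that it "is the current accepted clinical standard for diagnosis and monitoring of glaucomatous visual field loss". No other reference is named.
- **Population (VI.13).** "Patients older than 18 years of age with suspected, mild, moderate, or severe glaucoma". No control group is described.
- **Testing (I.4, VII.E.6).** Every subject takes both tests on the same day, in randomised order.
- **Analysis (XI.1).** Pointwise device-to-device comparison, with test points grouped by the Garway-Heath map. No defect criterion, structural measurement, adjudicated diagnosis, sensitivity or specificity is listed.
- **Power (XI.2).** 80 measurements per device "achieve 87% power to detect a difference between the device means", using a mixed-model test at the 0.05 level. No equivalence or agreement limit is given.
- **Disease severity.** I.4 lists it among the data to be recorded. It is not defined, has no reference role and does not appear among the XI.1 variables.

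**The concern.** The hypothesis makes two claims about detection: equal to the Humphrey, or better. Each needs something that the plan does not supply.

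*Better* needs a way to tell who is right when the devices disagree. If the headset reads lower at a location, the Humphrey may have missed a defect or the headset may have produced an artefact, and the planned data cannot separate the two. If the Humphrey defines truth, every disagreement counts against the headset. If it does not, the plan defines no truth.

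*As well as* needs a statement of how close is close enough. A test powered to find a difference does not provide one, because failing to find a difference is not evidence of equality.

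The form itself states that there is no separate protocol (VII.B.11) and that there are no prior studies of this device (VII.B.32), while IX.2 presents the expected benefit as validation. The hypothesis sentence is therefore the only statement of what a positive result would mean. A mean difference in either direction, or a non-significant one, could be reported as superior or equal detection of glaucoma.

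**Working it through.** **1. The plan's own power figure.** Inputs from XI.2: 80 measurements per device, in 40 clusters of average size 2; SD 0.25; intracluster correlation 0.5; alpha 0.05 (taken as two-sided, since sidedness is not stated).

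- Design effect = 1 + (2 − 1) × 0.5 = 1.5.
- SE of the device difference = 0.25 × √(2 × 1.5 / 80) = 0.0484.
- The difference is printed as 0. At exactly 0, the two-sided rejection probability is 5%, not 87%.
- Solving for 87%: (1.960 + 1.126) × 0.0484 = 0.149. At 0.15 the power is 87.3%.

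The intended difference was probably 0.15, with digits lost. This is an inference. The section reports formatting trouble and refers to an attached full calculation, so nothing here rests on the printed 0. What matters is that the calculation concerns a difference in means, not detection.

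**2. Does a non-significant difference show *as well as*?** Power to detect a true difference d is Φ(d/SE − 1.960). Take d = 0.10, an illustrative value in the plan's unstated units.

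- Printed inputs: 0.10 / 0.0484 = 2.066, so power is 54% and a real difference of 0.10 would be missed 46% of the time.
- The printed inputs treat the devices as independent groups, but every subject takes both tests. With between-device correlation r, assuming 80 paired measurements and design effect 1.5 on the differences, SE = 0.25 × √(2(1 − r)) × √(1.5 / 80).
- At r = 0.5, SE = 0.0342 and the miss rate is 17%. At r = 0.8, SE = 0.0217 and it is 0.4%.

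The documents do not give r, so the miss rate cannot be fixed. At any value of r, non-significance reflects precision as well as closeness, and only a pre-stated limit separates them.

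**3. Can *better* be shown with the Humphrey as reference?** Suppose the headset were error-free, and let the Humphrey have sensitivity s, specificity c and prevalence of true loss p. Scored against the Humphrey:

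- apparent sensitivity = ps / [ps + (1 − p)(1 − c)]
- apparent specificity = (1 − p)c / [(1 − p)c + p(1 − s)]

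With s = 0.80, c = 0.85, p = 0.5, sensitivity = 0.400 / 0.475 = 0.84 and specificity = 0.425 / 0.525 = 0.81. All values of s, c and p are assumptions:

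| p | s / c | Apparent sensitivity | Apparent specificity |
|---|---|---|---|
| 0.5 | 0.80 / 0.85 | 0.84 | 0.81 |
| 0.5 | 0.90 / 0.95 | 0.95 | 0.91 |
| 0.9 | 0.80 / 0.85 | 0.98 | 0.32 |
| 0.9 | 0.90 / 0.95 | 0.99 | 0.51 |

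Even a perfect headset scores below 1 on both measures, while the Humphrey scored against itself has 1 on both. The comparison cannot return *better*.

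**4. Would a one-sided non-inferiority margin be enough?** Not on its own. It needs a direction known to be worse, and a higher or lower reading has no such meaning without an independent reference. A two-sided limit does not need one.

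**The case against.** **Accuracy against the accepted standard is an ordinary design.** This stands. A reader might infer that nothing about detection can be learned here, but the documents do not support that. Field change is a perimetric finding, the Humphrey is the accepted clinical standard, and sensitivity and specificity relative to it could be estimated if a defect criterion were set. Only superiority is ruled out by having a single reference. Relative accuracy is merely unspecified.

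**Unaffected people may be enrolled.** This also stands. A reader might infer that there are none, but the population includes suspected glaucoma, and some suspects may have no field loss. The plan has no step to identify who is unaffected.

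**Severity is recorded and could serve as a second reference.** In principle, yes, but the plan gives it no definition or role and leaves it out of XI.1. If it were graded from Humphrey fields it would not be independent; its basis is not stated. The Garway-Heath map does not fill the gap either, because it only groups test points.

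**The harm is conjectural.** In part. Aim 1 is neutral, no rule for declaring superiority is written, and VIII.2 says that no treatment is directed by the study. But the sentence at issue is the primary hypothesis, and nothing elsewhere limits how it may be read.

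**Is the present size enough for an agreement test?** A reader might infer so from the power inputs. The documents do not settle it. For an illustrative limit of ±0.10 and a true difference of 0, two-sided equivalence power = 2Φ(0.10/SE − 1.645) − 1. That is 33% with the independent-group SE, and 80% and 99.7% with the paired SEs above. The correlation is unknown and the SD has no stated units, so no single power should be quoted. The 80 measurements per device also need linking to the planned enrolment, given as 50 subjects in I.4 and 52 in VI.1.

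**Conclusion.** The point holds in limited form. With the Humphrey as the only reference, the plan cannot conclude that the headset detects glaucomatous change better. With a difference test and no limit, it cannot conclude that the headset does so equally well. Both conclusions follow from the design and do not depend on the assumed figures above.

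The 46% miss rate at a difference of 0.10 follows from the plan's printed inputs, but it uses an SE that ignores pairing and is best read as an illustration. The apparent-accuracy table rests on assumed Humphrey error rates that are independent of the headset given true status. The plan remains able to estimate agreement with the Humphrey and, with a defect criterion, accuracy relative to it. The change should be made because it alters what the trial may claim.

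**What to change.** 1. **I.5.** Delete *or better*. Restate the hypothesis as agreement with the Humphrey, or as identification of field change relative to the Humphrey.
2. **XI.1.** Specify a within-subject paired analysis. Agreement is concluded if the 90% confidence interval for the mean headset-minus-Humphrey difference lies inside a pre-stated two-sided limit. Say whether this applies to each Garway-Heath sector or to one named summary measure.
3. **XI.1.** Report 95% limits of agreement alongside, because discrepancies of opposite sign can cancel in a mean.
4. **I.5 or XI.1.** State that no claim of superiority, or of absolute sensitivity or specificity, will be made. Accuracy relative to the Humphrey may be reported only with a defect criterion set in advance.
5. **XI.2.** If power for agreement is to be stated, base it on the paired design, with the limit, the units of the SD and the assumed between-device correlation given.

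The cost is wording, and the work of choosing and justifying an agreement limit. No patients, visits or procedures are added. The study gives up a superiority claim that it could not have supported.
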